### **6.3.1 Potential drug-induced liver injury IMP discontinuation criteria**

Subjects with potential drug-induced liver injury (PDILI) must be assessed to determine if IMP must be discontinued. In addition, all concomitant medications and herbal supplements that are not medically necessary should also be discontinued.

The PDILI criteria below require immediate and permanent discontinuation of IMP:

- Subjects with either of the following:
  - ALT or AST  $\geq 5$ xULN
  - ALT or AST  $\geq 3$ xULN and coexisting total bilirubin  $\geq 2$ xULN
  - Subjects with ALT or AST  $\geq 3$ xULN who exhibit temporally associated symptoms of hepatitis or hypersensitivity. Hepatitis symptoms include fatigue, nausea, vomiting, right upper quadrant pain or tenderness. Hypersensitivity symptoms include fever (without clear alternative cause), rash, or eosinophilia (ie,  $>5\%$ ).

The PDILI criterion below allows for subjects to continue on IMP at the discretion of the Investigator.

- Subjects with ALT or AST  $\geq 3$ xULN (and  $\geq 2$ x Baseline) and  $< 5$ xULN, total bilirubin  $< 2$ xULN, and no eosinophilia (ie,  $\leq 5\%$ ), with no fever, rash, or symptoms of hepatitis (eg, fatigue, nausea, vomiting, right upper quadrant pain or tenderness).

Evaluation of PDILI must be initiated as described in Section 12.5.1. If subjects are unable to comply with the applicable monitoring schedule, IMP must be discontinued immediately.

Investigators should attempt to obtain information on subjects in the case of IMP discontinuation to complete the final evaluation. Subjects with PDILI should not be withdrawn from the study until investigation and monitoring are complete. All results of these evaluations and observations, as well as the reason(s) for IMP discontinuation and subject withdrawal (if applicable), must be recorded in the source documents. The CRF must document the primary reason for IMP discontinuation.

## **7 STUDY TREATMENTS**

### **7.1 Description of investigational medicinal products**

The IMPs used in this study are bimekizumab and placebo.

Bimekizumab will be supplied as a clear to opalescent, colorless to slightly brown, sterile, preservative-free solution in 2mL Type I, colorless glass vials (1.0mL extractable volume)

closed with a rubber stopper and sealed with an aluminum cap overseal. [REDACTED]

Placebo will be supplied as 0.9% sodium chloride aqueous solution (physiological saline, preservative free) of pharmacopoeia (United States Pharmacopoeia/European Pharmacopoeia) quality appropriate for injection.

Further details of the study medications and their specifications are provided in the Investigational Medicinal Product Handling Manual.

## 7.2 Treatments to be administered

The IMP is to be administered in the clinic by study site staff as 2 sc injections. Suitable areas for sc injections are the lateral abdominal wall and upper outer thigh. During each dosing visit, each of the 2 injections should be administered at a separate injection site. Injection sites should be rotated and injections should not be given into areas where the skin is tender, bruised, red or hard.

Study medication (bimekizumab and placebo) will be administered at the times indicated in Table 5–1. The minimum time between doses during the Double-Blind Period should be no less than 25 days and no more than 31 days and during the Dose-Blind Period should be no less than 24 days and no more than 32 days.

An IMP Handling Manual will be provided to each site containing instructions regarding drug preparation and dosing.

## 7.3 Packaging

The IMPs are manufactured, packaged, and labeled according to Good Manufacturing Practice guidelines and applicable laws or regulations. Investigational medicinal products will be suitably packaged in such a way as to protect the IMPs from deterioration during transport and storage.

## 7.4 Labeling

Clinical drug supplies will be labeled in accordance with the current International Council on Harmonisation (ICH) guidelines on Good Clinical Practice (GCP) and Good Manufacturing Practice and will include any locally required statements. If necessary, labels will be translated into the local language.

## 7.5 Handling and storage requirements

Investigational Medicinal Product must be stored under refrigerated conditions (2°C to 8°C) protected from light. The IMP must not be frozen.

The Investigator (or designee) is responsible for the safe and proper storage of IMP at the site. Investigational medicinal product stored by the Investigator is to be kept in a secured area with limited access.

Appropriate storage conditions must be ensured either by controlled room temperature or by completion of a temperature log in accordance with local requirements on a regular basis (eg, once a week), showing minimum and maximum temperatures reached over the time interval.

In case an out-of-range temperature is noted, it must be immediately communicated to the Clinical Project Manager (CPM) (or designee) before further use of the IMP.

Investigational medicinal product will be shipped to the study sites in temperature controlled containers. Out-of-range shipping or storage conditions must be brought to the attention of the Sponsor or designee, immediately. Authorization to use any out-of-range IMP must be documented and received prior to dispensing or administering the IMP at the study site.

## 7.6 Drug accountability

A Drug Accountability form will be used to record IMP dispensing and return information on a by-subject basis and will serve as source documentation during the course of the study. Details of any IMP lost (due to breakage or wastage), not used, disposed of at the study site, or returned to the Sponsor or designee must also be recorded on the appropriate forms. All supplies and pharmacy documentation must be made available throughout the study for UCB (or designee) to review.

In order to maintain the blind, all IMP documentation (eg, shipping receipts, drug accountability logs, interactive voice or web response system (IXRS) randomization materials) must be maintained and accessed by unblinded, trained site personnel only. Designated, unblinded site personnel must be appropriately trained and licensed (per country guidelines) to administer injections.

The packaging identifies each kit by a unique number that does not correlate to the contents and therefore, does not unblind study site staff. Unblinded study staff will be responsible for preparation (breaking tamper proof sticker on kit, etc) of the clinical trial material, including recording the administration information in the source document.

The Investigator (or designee) is responsible for retaining all used, unused, and partially used containers of IMP until returned or destroyed.

The Investigator may assign some of the Investigator's duties for drug accountability at the study site to an appropriate pharmacist/designee.

The Investigator must ensure that the IMP is used only in accordance with the protocol.

Periodically, and/or after completion of the clinical phase of the study, all used (including empty containers) and unused IMP containers must be reconciled and returned to UCB (or designee), preferably in their original package. Onsite destruction of used kits only may be allowed with prior approval from the Sponsor or designee after reconciliation. Investigational medicinal product intended for the study cannot be used for any other purpose than that described in this protocol.

## 7.7 Procedures for monitoring subject compliance

During the Double-Blind and Dose-Blind Periods, IMP will be administered in the clinic and compliance will be determined at the visit by study personnel. Drug accountability must be recorded on the Drug Accountability Form.

## 7.8 Concomitant medication(s)/treatment(s)

All concomitant medications, including over-the-counter products, herbal, traditional remedies, vitamin/mineral supplements, other dietary supplements, "nutraceuticals," and hormones must be recorded in the subject's source documentation (eg, clinical chart) and in the electronic eCRF. This record should include the name of the drug, the dose, the route and date(s) of administration, and the indication for use.

### 7.8.1 Permitted concomitant treatments (medications and therapies)

No medication increases or additions are permitted for medications taken for PsA until after the Week 16 visit assessments. However, a decrease in dose or dosing frequency of any agent is permitted for reasons of intolerance/AEs/side-effects at any time.

At Week 16, Week 24, and Week 36 of the Dose-blind Period, subjects will be evaluated for their response to treatment to determine eligibility for rescue therapy.

Subjects who have shown <10% improvement from Baseline in TJC and SJC will be eligible for rescue therapy. Rescue therapy for eligible subjects will be at the Investigator's discretion, with the following options:

- Nonsteroidal anti-inflammatory drugs, DMARDs (MTX, sulfasalazine, LEF, apremilast), and/or joint injections may be given as rescue therapy if deemed appropriate by the Investigator as outlined below. Subjects may receive these add-on therapies while continuing to receive their randomized dose of bimekizumab.
  - For subjects taking NSAID/COX-2 inhibitors at Baseline or at Week 16, Week 24, or Week 36, a change can be made to a different NSAID/COX-2. Changes from an NSAID to a COX-2 or from a COX-2 to an NSAID are permitted up to the maximum approved or tolerated dose, whichever is lower. Only 1 NSAID/COX-2 may be taken at a given time.
  - For subjects not taking NSAID/COX-2 inhibitors at Baseline, Week 16, Week 24, or Week 36, either a NSAID or COX-2 inhibitor can be initiated, up to the maximum approved or tolerated dose, whichever is lower. Only 1 NSAID/COX-2 may be taken at a given time.
  - Methotrexate may be added or increased to a maximum dose of 25mg/week, or the maximum tolerated dose, whichever is lower. The route of administration may be changed from oral to sc.
  - Sulfasalazine may be given up to a maximum dose of 3g/day, or the maximum tolerated dose, whichever is lower.
  - Leflunomide may be given at a maximum dose of 20mg/day (or an average of 20mg/day if not dosed daily), or the maximum tolerated dose, whichever is lower.
  - Apremilast may be given at a maximum dose of 30mg twice daily, or the maximum tolerated dose, whichever is lower.
  - Combination DMARDs are allowed except that LEF and MTX may not be given together.
    - One joint may be injected at or after the Week 16, Week 24, and Week 36 Visit; however, the same joint should not be injected more than once during the study.

Subjects are allowed to use acetaminophen/paracetamol and mild opioids as needed.

Subjects who are already receiving an established antidepressant regimen should be on a stable dose of the antidepressant for 12 weeks prior to Baseline.

#### **Psoriasis treatments**

For treatment of PSO, subjects may continue to use topical moisturizers, emollients, salicylic acid preparations, bath oils, and oatmeal bath preparations for skin conditions during the study, as needed. Over-the-counter shampoos for the treatment of PSO of the scalp are also permitted. Additionally, mild topical steroids are permitted for use limited to the face, axillae, and/or genitalia, as needed. Subjects who use prohibited topical medications will be allowed to stay in the study but will be counseled to not use them further. No other topical preparations are allowed in the 2 weeks prior to randomization or during the study unless medically required to treat an AE. See [Table 7-2](#) for prohibited PSO medications.

After the Week 16 Visit, the addition of topical retinoids, vitamin D analogues, coal tar preparations, and more potent topical steroids may be used as medically required to treat a flare, but are not permitted to be used within 24 hours prior to a study visit. Use of psoralen and ultraviolet A light (PUVA/UVA) therapy for the treatment of PSO is not permitted for the first 16 weeks of the study and is discouraged through the duration of the study.

### 7.8.2 Prohibited concomitant treatments (medications and therapies)

Prohibited and/or restricted medications are summarized in [Table 7-1](#) and [Table 7-2](#).

**Table 7-1 Prohibited or restricted medications and required wash-out periods prior to Baseline**

Drug class	Dose	Exclusion criteria
Analgesics, including opioid analgesics, acetaminophen/paracetamol, etc	Any dose	Any ad hoc use in the 24 hours prior to any Study Visit. Stable doses of analgesics permitted.
NSAIDs/COX-2 inhibitors	Any dose regimen	Any change in dose/dose regimen in the 14 days prior to the Baseline Visit.
Oral corticosteroids	Any dose regimen	Any change in dose/dose regimen in the 28 days prior to the Baseline Visit.
Intramuscular/intravenous /intra-articular corticosteroids	Any dose	Use in the 28 days prior to the Baseline Visit.
Intra-articular hyaluronic acid	Any dose	Use in the 6 months prior to the Baseline Visit.
DMARDs: -hydroxychloroquine, -azathioprine, -cyclosporine, -cyclophosphamide, -mycophenolic acid -mycophenolate mofetil -sulfasalazine (SSZ) a -any other small molecule DMARDs (eg, tofacitinib, apremilast a )	Any dose	Use within 12 weeks prior to the Baseline Visit.
-methotrexate (MTX)	Any dose regimen	Use within 12 weeks prior to the Baseline Visit unless Inclusion Criterion #11 is met.

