#### **5.1.4 Rescue therapy**

At [Week 16](#), [Week 24](#), and [Week 36](#) of the Dose-blind Period, subjects will be evaluated for their response to treatment to determine eligibility for rescue therapy.

Subjects who have shown <10% improvement from Baseline in TJC and SJC will be eligible for rescue therapy. Rescue therapy for eligible subjects will be at the Investigator's discretion, with the following options:

- Nonsteroidal anti-inflammatory drugs, DMARDs (MTX, sulfasalazine, LEF, apremilast), and/or joint injections may be given as rescue therapy if deemed appropriate by the Investigator as outlined below. Subjects may receive these add-on therapies while continuing to receive their randomized dose of bimekizumab.
  - For subjects taking NSAID/COX-2 inhibitors at Baseline or at [Week 16](#), [Week 24](#), or [Week 36](#), a change can be made to a different NSAID/COX-2. Changes from an NSAID to a COX-2 or from a COX-2 to an NSAID are permitted up to the maximum approved or tolerated dose, whichever is lower. Only 1 NSAID/COX-2 may be taken at a given time.
  - For subjects not taking NSAID/COX-2 inhibitors at Baseline, [Week 16](#), [Week 24](#), or [Week 36](#), either a NSAID or COX-2 inhibitor can be initiated, up to the maximum approved or tolerated dose, whichever is lower. Only 1 NSAID/COX-2 may be taken at a given time.
  - Methotrexate may be added or increased to a maximum dose of 25mg/week, or the maximum tolerated dose, whichever is lower. The route of administration may be changed from oral to sc.
  - Sulfasalazine may be given up to a maximum dose of 3g/day, or the maximum tolerated dose, whichever is lower.
  - Leflunomide may be given at a maximum dose of 20mg/day (or an average of 20mg/day if not dosed daily), or the maximum tolerated dose, whichever is lower.

- Apremilast may be given at a maximum dose of 30mg twice daily, or the maximum tolerated dose, whichever is lower.
- Combination DMARDs are allowed except that LEF and MTX may not be given together.
- One joint may be injected at or after the Week 16, Week 24, and Week 36 Visit; however, the same joint should not be injected more than once during the study.
- A decrease in dose or dosing frequency of any agent for the treatment of PsA is permitted for reasons of intolerance/AEs/side-effects at any time.

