### 9.1 TJC and SJC

#### 9.1.1 78/76 joint evaluation for ACR response and verification of Inclusion Criterion 5

The Principal Investigator, another delegated physician, or an appropriately qualified medical professional (based on local requirements) who has had documented training on how to perform these assessments correctly assesses the following joints for tenderness: the distal interphalangeal, proximal interphalangeal and metacarpophalangeal joints of the hands, and metatarsophalangeal joints of the feet, the carpometacarpal and wrist joints (counted separately), the elbows, shoulders, acromioclavicular, sternoclavicular, hip, knee, talo-tibial, and midtarsal joints. All of these except for the hips are assessed for swelling.

Artificial and ankylosed joints, as well as missing joints (ie, amputated joints), are excluded from both tenderness and swelling assessments.

One dactylitic digit is to be counted as 1 swollen joint (instead of counting as 3 in the finger or 2 in the toe).

Table 9-1 summarizes the swelling and tenderness grading criteria.

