2 PROTOCOL SUMMARY

This is a Phase 2b, multicenter, randomized, double-blind, placebo-controlled, parallel-group, dose-ranging study to investigate the efficacy, safety, pharmacokinetics (PK), and pharmacodynamics (PD) of bimekizumab (also known as UCB4940) compared with placebo in adult subjects with active psoriatic arthritis (PsA) in order to guide the selection of doses and clinical indices in the Phase 3 development program.

The study population will consist of adult subjects (≥ 18 years of age) fulfilling the Classification Criteria for Psoriatic Arthritis (CASPAR, Table 12-1) criteria and having active disease with tender joint count (TJC) ≥ 3 out of 78 and swollen joint count (SJC) ≥ 3 out of 76. Subjects must be rheumatoid factor and anti-cyclic citrullinated peptide (CCP) antibodies negative and have active psoriatic lesion(s) and/or a documented history of psoriasis. Subjects may be tumor necrosis factor (TNF) inhibitor naïve or may have received 1 prior TNF inhibitor.

Subjects who have been on a TNF inhibitor previously must have:

- experienced an inadequate response to previous treatment given for at least 3 months
- been intolerant to administration (eg, had a side-effect/adverse event (AE) that led to discontinuation)
- lost access to TNF inhibitor for other reasons

An estimated 70 sites in Europe and North America will randomize 200 subjects. Enrollment of TNF inhibitor experienced subjects will be limited to 30% of the total study population.

The study consists of a Screening Period (14 to 28 days), Double-Blind Period (12 weeks), Dose-Blind Period (36 weeks) and Safety Follow-up Period (20 weeks after last dose; only for subjects who do not enter the extension study). Therefore, the maximum duration of the study is 68 weeks.

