8.1.1.1 Tender joint count (TJC) and swollen joint count (SJC)

8.1.1.1.1 78/76 joint evaluation for ACR response

The Principal Investigator, another delegated physician, or an appropriately qualified medical professional (based on local requirements) who has had documented training on how to perform these assessments correctly assesses the following joints for tenderness: the distal interphalangeal, proximal interphalangeal and metacarpophalangeal joints of the hands, and metatarsophalangeal joints of the feet, the carpometacarpal and wrist joints (counted separately), the elbows, shoulders, acromioclavicular, sternoclavicular, hip, knee, talo-tibial, and midtarsal joints. All of these except for the hips are assessed for swelling.

Artificial and ankylosed joints, as well as missing joints (ie, amputated joints), are excluded from both tenderness and swelling assessments.

One dactylitic digit is to be counted as 1 swollen joint (instead of counting as 3 in the finger or 2 in the toe).

[Table 8–1](#) summarizes the swelling and tenderness grading criteria.

Table 8–1: Swelling and tenderness grading

The tender joint counts (TJC) and swollen joint counts (SJC) are weighted joint counts. If there are missing observations in the tender or swollen joint assessments, then the remaining observations will be assessed and weighted by the number of the assessed joints (AJ):

$$SJC = n * \sum_{i=1}^n SJ / \sum_{i=1}^n AJ \tag{9}$$

$$TJC = n * \sum_{i=1}^n TJ / \sum_{i=1}^n AJ \tag{10}$$

where n is the number of total joints. If a joint is missing at Baseline, then that joint is set to missing throughout the study. If more than 50% of the tender joint assessments or 50% of the

swollen joint assessments are missing at the time of a given assessment, then no imputation will be done and the total TJC or SJC will be set to missing for that visit.

Injected joints will be counted as swollen and tender from the date of injection up to 52 weeks after injection, ie, swelling and tenderness grading is 1.

8.1.1.1.2 28 joint evaluation for determination of DAS28(CRP)

The following 28 joints will be used for calculation of the DAS28(CRP).

- Upper extremity (26)-bilateral shoulders, elbows, wrists (includes radiocarpal, and carpal and carpometacarpal bones considered as a single unit), MCP I, II, III, IV, and V, thumb interphalangeals (IP), PIP II, III, IV, and V
- Lower extremity (2)-knees

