13.1.1 Rationale for the amendment

The main objectives of this SAP amendment are to describe and specify the extension of time point up to Week 24 for the interim analysis. The SAP has been amended to:

- Add additional analyses for the time points up to Week 24 for ACR, PASI, MDA, TEAEs, Hy's Law, PK, and AbAb data
- Add the definition for rheumatoid factor and anti-CCP antibodies positivity and negativity
- Add clarification for handling injected joints for the swollen and tender grading
- Add assessment of potential bias of potentially unblinding at the entry of Dose-Blind phase
- Refine the categories of the subgroup variable Psoriasis BSA

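### The SAP's 52-week injected-joint rule is not limited to on-study injections, so as written it also fixes the score of joints injected before Baseline (minor)

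*Protocol*

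**What the plan says.** - **Scoring rule.** SAP 8.1.1.1.1 (78/76 count) states: "Injected joints will be counted as swollen and tender from the date of injection up to 52 weeks after injection". SAP 8.1.1.1.2 repeats this for the 28-joint count used in DAS28(CRP). Neither names a study period, an earliest date or an injected agent. SAP Amendment 1 introduced the rule, giving as its reason: "Add clarification for handling injected joints for the swollen and tender grading".
- **Injections before the study.** In Protocol Table 7-1 the exclusion for intra-articular corticosteroid reads "Use in the 28 days prior to the Baseline Visit", and for intra-articular hyaluronic acid "Use in the 6 months prior to the Baseline Visit". Both periods are shorter than 52 weeks.
- **Injections on study.** Protocol 5.1.4 allows them only as rescue: "One joint may be injected at or after the Week 16, Week 24, and Week 36 Visit". Protocol 7.8.1 adds: "No medication increases or additions are permitted for medications taken for PsA until after the Week 16 visit assessments".
- **Joints left out of the counts.** Protocol 9.1.1: "Artificial and ankylosed joints, as well as missing joints (ie, amputated joints), are excluded from both tenderness and swelling assessments". Injected joints are not on that list.
- **Entry minimum.** SAP Section 2: "tender joint count (TJC) ≥ 3 out of 78 and swollen joint count (SJC) ≥ 3 out of 76".

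**The concern.** The protocol permits no joint injection between Baseline and Week 12. Read literally, the only permitted injections that can trigger the rule at the two visits behind the primary endpoint are therefore those given before the study. For these the SAP replaces the examination of that joint with a fixed score of 1. The Baseline definition in SAP 3.3 does not override this.

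Tender and swollen counts must both improve by 50% for ACR50 (SAP 8.1.1), and entry needs only three of each. One fixed joint can therefore alter a subject's responder status. The same counts feed ACR20, ACR70, DAS28(CRP) and MDA. MDA lists a tender count and a swollen count of at most 1 as separate criteria, so a single fixed joint uses up both allowances. The error runs in two directions, depending on when the joint was injected.

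**Working it through.** **1. The plan's own figure.** Protocol 15.9 and SAP 2.4 state power above 99% for the linear-trend test with 40 per arm, two-sided 0.05. The assumed ACR50 rates are 8%, 15.0%, 42.2% and 58.5%, with a 25% reduction in 30% of subjects. Reading that reduction as relative, the factor is 1 − 0.25 × 0.30 = 0.925, giving 7.4%, 13.9%, 39.0% and 54.1%. A normal-approximation trend test on four groups with equal scores has power 99.99% (99.98% with a continuity correction). The stated figure reproduces.

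**2. Which injection dates matter.** The rule lasts 52 × 7 = 364 days and Week 12 is day 84 after Baseline. An injection *d* days before Baseline is covered at Baseline if *d* ≤ 364, and at Week 12 if *d* ≤ 364 − 84 = 280. The corticosteroid washout allows *d* ≥ 29.

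| Injected before Baseline | Baseline | Week 12 |
|---|---|---|
| 29 to 280 days | fixed at 1 | fixed at 1 |
| 281 to 364 days | fixed at 1 | examined |

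**3. Fixed at both visits, joint quiet on examination.** Let T be the other active joints at Baseline and R those still active at Week 12. The 50% criterion becomes R + 1 ≤ 0.5(T + 1), so R ≤ (T − 1)/2 instead of R ≤ T/2.

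| T | Must clear, as examined | Must clear, under the rule |
|---|---|---|
| 3 | 2 | 2 |
| 4 | 2 | 3 |
| 6 | 3 | 4 |
| 10 | 5 | 6 |
| 15 | 8 | 8 |
| 20 | 10 | 11 |

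Odd T is unaffected; even T needs one more joint cleared.

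**4. Fixed at both visits, joint truly active at Baseline.** With a count of 3 including the injected joint, the largest scorable improvement is 2/3 = 66.7%. ACR50 is still reachable but ACR70 is not. A subject who clears the injected joint and one other has improved by 2/3 = 66.7% but scores 1/3 = 33.3% and misses ACR50. If two of the three were injected, the maximum is 33.3% and ACR50 is out of reach.

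**5. Fixed at Baseline only, joint quiet throughout.** The criterion becomes R ≤ (T + 1)/2. At T = 3, two residual joints pass: the true improvement is 1/3 = 33.3% and the scored one is 2/4 = 50%. With no change at all in the other joints, the scored improvement is 1/(T + 1): 25% at T = 3, 14.3% at T = 6 and 9.1% at T = 10. For the 50% threshold, even T is unaffected.

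**6. Effect on power.** The documents do not give the share of subjects with such a history. Assume 5% to 30% (10 to 60 of 200), with 25% to 100% of their responses lost equally in every arm. Trend power (four groups, equal scores, no continuity correction) is then 98.8% to 99.98%. Power for 160mg versus placebo, which the plan does not state, is 93.3% with no loss and 92.9% to 77.6% over the same range. The low end requires 30% affected and every one of their responses lost.

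**7. Whether limiting the rule changes rescue handling.** The earliest permitted injection is at Week 16, and 16 + 52 = Week 68. The last joint count is at Week 48 or at the Safety Follow-Up Visit, 20 weeks after the Week 44 dose, about Week 64. For permitted on-study injections the 52 weeks outlast every joint count, so a date limit leaves them untouched.

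**The case against.** The best defence is that the sentence was meant for rescue injections. They are the only joint injections the protocol provides for, the amendment calls the text a clarification, and Week 68 matches the 68-week maximum study duration. This is plausible but not stated. The 68-week maximum includes up to 4 weeks of Screening (4 + 44 + 20), so it ends at about Week 64 after Baseline. For permitted on-study injections the 52-week limit never takes effect; among permitted injections, it can expire during the study only for one given before it.

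A second defence is that the rule may be impossible to apply to earlier injections. Protocol 7.8 lists drug, dose, route, dates and indication for concomitant medications, and 13.4 requires prior medications to be recorded. Neither mentions which joint was injected, and the body of the grading table is not visible in the public copy. This stands as an uncertainty: without joint-level records the program cannot fix a pre-study joint. The text would still need its scope stated.

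Third, the effect is small and should be balanced, because injection history precedes randomization. That stands and sets the severity.

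**Conclusion.** The point holds in limited form and is minor. As worded, the rule reaches joints injected before the study and gives them a score that may contradict the examination at Baseline, or at both Baseline and Week 12. It can misclassify individual subjects on the ACR responses, DAS28(CRP) and MDA. How many cannot be sized from the documents; the shares above are assumptions.

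A reader might infer more, and the documents do not support it:

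- *That Baseline and Week 12 counts as a whole are set by rule.* Only the injected joint is fixed, only in subjects with that history, and at Week 12 only for injections within 280 days before Baseline.
- *That one fixed joint always changes responder status.* A quiet joint fixed at both visits changes nothing for ACR50 at odd counts such as 3 or 15.
- *That the washout in Table 7-1 is the defect.* It only shows how the situation can arise; the missing limit is in the SAP.
- *That the primary analysis is at risk.* No imbalance between arms is expected, and trend power stays at 98.8% or more across the assumed range.

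**What to change.** Add to SAP 8.1.1.1.1 and 8.1.1.1.2, directly after the existing sentence:

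*This rule applies only to joints injected on or after the first dose of study medication; joints injected before the first dose are scored as examined.*

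Leave the 52-week duration and Table 7-1 unchanged. The cost is one sentence in two subsections and a date condition in the derivation program. No new data are needed.
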